# Clinical Study Protocol

## Johnson & Johnson Vision Care, Inc.

parameters ( $\beta_0, \beta_1, \rho$ ). Inferences will be made based on a posterior credible interval for the relevant parameters.

### ***Bayesian Estimation and Statistical Evaluation of Hypothesis:***

Superiority of the Test lens relative to the pre-defined threshold with respect to Grade 3 or higher will be evaluated using Bayesian statistics.

### **Primary Safety Hypothesis 1:**

The null and alternative hypotheses for evaluating superiority of the Test lens relative to 5% are as follows:

$$H_0: p_T \geq 0.05$$
$$H_A: p_T < 0.05,$$

where  $p_T$  is the probability of a Grade 3 or higher SLF across all study visits for Test lens. Based on Bayesian posterior probability distribution of the proportion  $p_T$ , superiority is interpreted as 95% probability of Test being statistically lower than the threshold of 5% (i.e.,  $p_T < 0.05$ ). If the upper bound of the 95% central posterior credible interval is below 0.05, it can be concluded that there is 95% probability that the Test lens is superior to 5% (statistically less than) based on the observed sample.

In the case of zero clinically significant SLF, a Bayesian hierarchical model accounting for zero event problem will be considered.

### ***Unacceptable Lens Fitting***

Lens fit acceptance will be analyzed using a Bayesian beta-binomial model with correlated binary data.

### ***Bayesian Estimation and Statistical Evaluation of Hypothesis:***

Superiority of the Test lens relative to the pre-defined threshold with respect to unacceptable lens fitting will be evaluated using Bayesian statistics.

### **Primary Safety Hypothesis 2:**

The null and alternative hypotheses for evaluating superiority of the Test lens relative to 5% are as follows:

$$H_0: p_T \geq 0.05$$
$$H_A: p_T < 0.05,$$

where  $p_T$  is the probability of event (i.e., probability of unacceptable lens fitting while wearing the test lens). Based on Bayesian posterior probability distribution of the proportion  $p_T$ , superiority is interpreted as 95% probability of the Test lens being statistically lower than the pre-defined threshold of 5% (i.e.,  $p_T < 0.05$ ) with respect to unacceptable lens fitting rate. If the upper bound of the 95% central posterior credible interval is below 0.05, it can be

# Clinical Study Protocol

## Johnson & Johnson Vision Care, Inc.

concluded that there is 95% probability that the Test lens is superior to the 5% threshold (statistically less) based on the observed sample.

In the case of all eyes have an acceptable lens fit (i.e., zero unacceptable lens fit), a Bayesian hierarchical model accounting for zero event problem will be considered. Details of this model will be provided in the stand-alone SAP.

### **Primary Efficacy Analyses:**

All primary efficacy analyses will be conducted on the intent-to-treat population.

Threshold utilized in hypothesis testing related to CLUE vision scores were based on a meta-analysis of CLUE vision scores for the Market leader for multifocal lenses, Air Optix.

### ***CLUE Vision Scores***

Mean population estimates and two-sided 95% confidence intervals will be computed separately for each stratum (hyperopes and myopes) using a bootstrap methodology. At least a total of 20000 bootstrap iterations will be used following the suggestions of Samuelson and Petrick. A minimum threshold of 4000 bootstrap iterations was recommended for an alpha=0.05, however, since each test will be performed using alpha=0.01, it is more appropriate to increase number of bootstrap iterations. The assessment of the impact of the autocorrelation for between subjects repeated measurements, is defined by the difference between the observed statistic compared to the bootstrapped population mean (bias= observed minus bootstrapped population mean). This approach was recommended for all estimations of statistical inference since this approach accommodates correlated data. The bootstrap analysis that will be performed followed a procedure as discussed by Davison, AC and Hinkley, DV.

### **Primary Efficacy Hypothesis 1:**

The null and alternative hypothesis to test for superiority of Myopes relative to the threshold 41 CLUE points are as follows:

$$H_0: \mu_{Test} \leq 41$$

$$H_A: \mu_{Test} > 41$$

Where  $\mu_{Test}$ , represents the population mean for Myopes at the 1-week follow-up with respect to CLUE vision scores. Superiority will be declared if the lower limit of the 95% CI is above 41.

### **Primary Efficacy Hypothesis 2:**

The null and alternative hypothesis to test for superiority of Hyperopes relative to the threshold 36 CLUE points are as follows:

$$H_0: \mu_{Test} \leq 36$$

$$H_A: \mu_{Test} > 36$$

# Clinical Study Protocol

## Johnson & Johnson Vision Care, Inc.

Where  $\mu_{Test}$ , represents the population mean for Hyperopes at the 1-week follow-up with respect to CLUE vision scores. Superiority will be declared if the lower limit of the 95% CI is above 36.

### **Visual Performance (logMAR)**

Binocular HLHC visual performance will utilize the same bootstrapping methodology as described above for CLUE vision. However, with respect to VP, mean population estimates and two-sided 95% confidence intervals will be computed separately for each distance (distance 4m, intermediate 64cm and near 40cm) but will combine the hyperopic and myopic populations. At least a total of 20000 bootstrap iterations will be used following the suggestions of Samuelson and Petrick. A minimum threshold of 4000 bootstrap iterations was recommended for an alpha=0.05, however, since each test will be performed using alpha=0.01, it is more appropriate to increase number of bootstrap iterations. The assessment of the impact of the autocorrelation for between subjects repeated measurements, is defined by the difference between the observed statistic compared to the bootstrapped population mean (bias= observed minus bootstrapped population mean). This approach was recommended for all estimations of statistical inference since this approach accommodates correlated data. The bootstrap analysis that will be performed followed a procedure as discussed by Davison, AC and Hinkley, DV.

### **Primary Efficacy Hypothesis 3:**

The null and alternative hypothesis for binocular distance HLHC visual performance to test for superiority of Aurora relative to the threshold 0.0 logMAR are as follows:

$$H_o: \mu_{Test} \geq 0 \text{ logMAR}$$
$$H_A: \mu_{Test} < 0 \text{ logMAR}$$

Where  $\mu_{Test}$ , represents the population mean for Aurora at the 1-week follow-up with respect to distance HLHC visual performance. Superiority will be declared if the upper limit of the 95% CI is below 0.0.

### **Primary Efficacy Hypotheses 4 and 5:**

The null and alternative hypothesis for binocular intermediate and near HLHC visual performance to test for superiority of Aurora relative to the threshold 0.17 logMAR are as follows:

$$H_o: \mu_{Test} \geq 0.17 \text{ logMAR}$$
$$H_A: \mu_{Test} < 0.17 \text{ logMAR}$$

Where  $\mu_{Test}$ , represents the population mean for Aurora at the 1-week follow-up with respect to HLHC visual performance. Superiority will be declared if the upper limit of the 95% CI for either intermediate or near is below 0.17.

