### Co-Primary Efficacy Hypotheses:

1. After approximately 1-week of wear in the optimized Test lenses, the mean overall quality of vision score of the Test lenses will be statistically better than 41 points for the myope population. This will be recorded by the subject using the CLUE Follow-up Questionnaire.
2. After approximately 1-week of wear in the optimized Test lenses, the mean overall quality of vision score for the Test lenses will be statistically better than 36 points for the hyperope population. This will be recorded by the subject using the CLUE Follow-up Questionnaire.
3. After approximately 1-week of wear in the optimized Test lenses, the mean distance, binocular, high luminance, high contrast logMAR visual acuity score of the Test lens will be statistically lower than 0.0 logMAR.
4. After approximately 1-week of wear in the optimized Test lenses, the mean intermediate, binocular, high luminance, high contrast logMAR visual acuity score of the Test lens will be statistically lower than 0.17 logMAR.
5. After approximately 1-week of wear in the optimized Test lenses, the mean near, binocular, high luminance, high contrast logMAR visual acuity score of the Test lens will be statistically lower than 0.17 logMAR.

All safety and efficacy co-primary hypotheses must be satisfied in order to meet the study objectives and to test any secondary hypotheses.

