### 14.4. Level of Statistical Significance

All *co-primary safety*, *co-primary efficacy* and *secondary* hypotheses will be tested using a multibranch gate keeping strategy. Study hypotheses will be evaluated sequentially as follows: First, co-primary safety hypotheses will be tested using 95% central posterior credible intervals for the probability of Grade or higher and unacceptable lens fitting. Both hypotheses must be met in order to test co-primary efficacy hypotheses. Since both hypotheses must pass to continue testing primary hypotheses, an overall family-wise type I error rate of 5% will be allocated to co-primary efficacy hypotheses using a Bonferroni approach. Each co-primary efficacy hypothesis will be tested using two-sided type I error rate of 1% (5 hypotheses total

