# Clinical Study Protocol

## Johnson & Johnson Vision Care, Inc.

=5%). All co-primary safety and co-primary efficacy hypotheses must be met to test any secondary hypotheses.

*Secondary hypotheses* (except for lens fit success) will be tested with using an overall two-sided family-wise type I error rate of 5% (1% individually). Lens fit success will be tested using a 99% credible interval.

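### The decision sentence for co-primary efficacy Hypotheses 4 and 5 reads as an OR rule, which conflicts with the all-must-pass rule in sections 2.3 and 14.4

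*Combined protocol and SAP*

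**What the plan says.** Section 2.3 numbers intermediate and near acuity as separate co-primary efficacy hypotheses. Hypothesis 4 is that "the mean intermediate, binocular, high luminance, high contrast logMAR visual acuity score of the Test lens will be statistically lower than 0.17 logMAR", and Hypothesis 5 is that "the mean near, binocular, high luminance, high contrast logMAR visual acuity score of the Test lens will be statistically lower than 0.17 logMAR". The same section closes with the success criterion: "All safety and efficacy co-primary hypotheses must be satisfied in order to meet the study objectives and to test any secondary hypotheses".

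Section 14.4 sets the error rate hypothesis by hypothesis: "Each co-primary efficacy hypothesis will be tested using two-sided type I error rate of 1% (5 hypotheses total", adding to 5%. It then repeats the joint requirement: "All co-primary safety and co-primary efficacy hypotheses must be met to test any secondary hypotheses".

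Section 14.5 supplies the decision rules. Hypotheses 1, 2 and 3 each have their own; for distance acuity it is "Superiority will be declared if the upper limit of the 95% CI is below 0.0". Hypotheses 4 and 5 share one heading, one null and alternative, one symbol for the mean and one rule: "Superiority will be declared if the upper limit of the 95% CI for either intermediate or near is below 0.17". No other sentence in the document gives an interval criterion for these two hypotheses.

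**The concern.** In ordinary English, declaring superiority if the limit for *either* of two endpoints is below the threshold means that one is enough. Sections 2.3 and 14.4 need both. The two rules give different answers whenever intermediate passes and near does not.

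That is also the likelier way for the pair to split. Near has the smaller planned margin (0.67 SD, against 1.72 SD for intermediate), so the literal rule lets the easier endpoint carry the harder one. A primary decision rule should have one reading fixed in advance. With two available, the choice of what to declare for Hypotheses 4 and 5 could be made after the near result is known. Section 14.1 also says that a stand-alone SAP will follow, and it could copy the sentence.

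**Working it through.** **1. Which rule does the plan's own power figure imply?** Section 14.2 states about 99% power for each of the five efficacy hypotheses and about 95% combined.

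- All five must pass, independence assumed: 0.99^5 = 0.951. This reproduces the stated 95%.
- Hypotheses 4 and 5 joined by OR: 0.99^3 × (1 − 0.01^2) = 0.970.
- With the individual powers in Table 8, all five passing gives 0.994 × 0.993 × 0.990 × 0.994 × 0.990 = 0.962. With OR for the pair it is 0.994 × 0.994 × 0.990 × (1 − 0.007 × 0.010) = 0.978.

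The error allocation is also five-way: 5 × 1% = 5%. The planning was therefore done with both distances required.

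**2. Inputs for the size of the disagreement.** From Table 7: intermediate mean −0.024, SD 0.1129; near mean 0.085, SD 0.1264. The threshold is 0.17 for both. The number analysed is taken as 100, the completer target in section 14.2. The planned bootstrap interval is approximated by a one-sample t interval. Results are shown for 95% (as written in section 14.5) and 99% (matching the two-sided 1% in section 14.4).

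- Intermediate margin: (0.17 + 0.024)/0.1129 = 1.72 SD.
- Near margin: (0.17 − 0.085)/0.1264 = 0.67 SD.

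**3. When does near fail?** The standard error is 0.1264/√100 = 0.01264. The interval half-width is 0.0251 (95%) or 0.0332 (99%). Near fails when its observed mean is above 0.17 − 0.0251 = 0.145 or 0.17 − 0.0332 = 0.137.

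**4. How often do the two readings differ?** At its planning value, intermediate passes with probability 1.000 at either level. The readings therefore differ exactly when near fails: P(differ) = 1 − P(near upper limit < 0.17), from the noncentral t distribution.

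| True near mean | Near passes, 95% / 99% CI | Readings differ, 95% / 99% CI |
|---|---|---|
| 0.085 (planned) | 0.999999 / 0.99997 | <0.01% / <0.01% |
| 0.12 | 0.975 / 0.905 | 2.5% / 9.5% |
| 0.14 | 0.652 / 0.404 | 35% / 60% |
| 0.15 | 0.347 / 0.154 | 65% / 85% |
| 0.17 (null) | 0.025 / 0.005 | 97.5% / 99.5% |

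In the last row the literal rule declares the pair superior about 100% of the time; requiring both does so 2.5% or 0.5% of the time. The intermediate–near correlation, which the documents do not give, does not matter here because intermediate always passes. Simulation of 20,000 trials at assumed correlations of 0, 0.5 and 0.8 gave 1.000 for OR, and 0.024–0.026 (95%) or 0.0046–0.0052 (99%) for AND.

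**5. Both means at 0.17.** Over an assumed correlation of 0 to 0.9 (bivariate normal), the OR rule passes falsely 4.9% down to 3.5% of the time with 95% intervals, and 1.0% down to 0.75% with 99% intervals. The AND rule does so 0.06% up to 1.5%, and 0.003% up to 0.25%.

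**The case against.** The best defence is that the sentence is shorthand for two parallel tests. The heading is plural, and one symbol cannot stand for two different means, so the template must be applied once per distance. Section 14.5 also says that "two-sided 95% confidence intervals will be computed separately for each distance (distance 4m, intermediate 64cm and near 40cm"). On that reading, superiority is declared for whichever distance meets its own limit, and the joint requirement is left to sections 2.3 and 14.4, just as it is for Hypotheses 1 to 3. Nothing then conflicts.

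Two further points support the defence. No consequence is attached to a declaration for the pair: a failed near test fails the study and closes the secondary gate under either reading. And divergence is remote, since the near means reported for the seven earlier studies in section 1.5 run from 0.057 to 0.091, well short of the 0.137 to 0.145 at which near would fail.

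Much of this stands. The distributive reading is possible, the intent is AND, and this is probably a drafting slip. What does not follow is that the text is sound. The reader reaches the right rule only by overriding the plain words of the one sentence that states the criterion. Hypotheses 1 to 3 need no such repair, because each rule names a single endpoint.

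**Conclusion.** The concern holds. As written, the rule for Hypotheses 4 and 5 is an OR rule; sections 2.3 and 14.4 and the combined power in section 14.2 all require AND. The consequence is limited to a conflicting or disputed superiority declaration for intermediate and near, because the success criterion in section 2.3 and the gate in section 14.4 still control the study outcome.

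Under planning values the wording makes practically no difference. It becomes material if the true near mean lies roughly between 0.12 and 0.17, where the disagreement probability rises from 2.5% to 97.5% (95% interval) or from 9.5% to 99.5% (99% interval). These figures assume 100 analysed subjects, the Table 7 SDs, intermediate at its planned mean, and a t interval in place of the bootstrap. The point should be fixed, but it does not threaten the design.

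**What to change.** Replace the shared sentence in section 14.5 with separate rules, giving each distance its own symbol for the mean:

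- Hypothesis 4 is met if the upper confidence limit for the intermediate mean is below 0.17 logMAR.
- Hypothesis 5 is met if the upper confidence limit for the near mean is below 0.17 logMAR.
- Both are required.

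State a confidence level that matches the two-sided 1% in section 14.4. The 95% level now printed is a separate discrepancy, and this point does not depend on it, but the new sentences should not carry it forward. Use identical wording in the stand-alone SAP, and make the change before the near results are seen.

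The cost is a few lines of text, with no change to data collection or sample size. Requiring both distances loses almost nothing: under Table 7 values with 100 subjects, near power is 99.997% with a 99% interval and over 99.999% with a 95% interval.

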# Clinical Study Protocol

## Johnson & Johnson Vision Care, Inc.

### 14.6. Secondary Analysis

All secondary analyses will be conducted on the Intent-to-Treat population. Threshold utilized in hypothesis testing related to CLUE vision, comfort and handling scores were based on a meta-analysis of CLUE vision, comfort and handling scores for the Market leader for multifocal lenses, Air Optix.

#### ***CLUE Vision***

Secondary hypotheses 1 and 2 will be tested using the same estimates and 95% CIs from the analysis as described for CLUE Vision in section 14.5. The hypotheses tests will be performed separately for Hyperopes and Myopes using 2-sided 95% confidence intervals constructed for the population mean at the 1-week follow-up evaluation.

#### **Secondary Hypothesis 1:**

The null and alternative hypothesis to test for superiority of Myopes relative to the threshold 46 CLUE points are as follows:

$$H_0: \mu_{Test} \leq 46$$
$$H_A: \mu_{Test} > 46$$

Where  $\mu_{Test}$ , represents the population mean for Aurora Hyperopes at the 1-week follow-up with respect to CLUE vision scores. Superiority will be declared if the lower limit of the 95% CI is above 46.

#### **Secondary Hypothesis 2:**

The null and alternative hypothesis to test for superiority of Hyperopes relative to the threshold 41 CLUE points are as follows:

$$H_0: \mu_{Test} \leq 41$$
$$H_A: \mu_{Test} > 41$$

Where  $\mu_{Test}$ , represents the population mean for Aurora Hyperopes at the 1-week follow-up with respect to CLUE vision scores. Superiority will be declared if the lower limit of the 95% CI is above 41.

#### ***CLUE Comfort and Handling***

Mean population estimates and 95% CIs for CLUE comfort and handling will be calculated separately using bootstrapping techniques. For both comfort and handling scores, a minimum of 20000 bootstrap iterations will be used following the suggestions of Samuelson and Petrick. A minimum threshold of 4000 bootstrap iterations was recommended for an alpha=0.05, however, since each test will be performed using alpha=0.01, it is more appropriate to increase number of bootstrap iterations. The assessment of the impact of the autocorrelation for between subjects repeated measurements, is defined by the difference between the observed statistic compared to the bootstrapped population mean (bias= observed

# Clinical Study Protocol

## Johnson & Johnson Vision Care, Inc.

minus bootstrapped population mean). This approach was recommended for all estimations of statistical inference since this approach accommodates correlated data. The bootstrap analysis that will be performed followed a procedure as discussed by Davison, AC and Hinkley, DV. Secondary hypotheses 3 and 4 will be tested using the data from hyperopes and myopes combined since there is not a significant difference in performance between these two populations. The hypotheses tests will be performed separately for Comfort and Handling using 2-sided 95% confidence intervals constructed for the population means at the 1-week follow-up evaluation.

### **Secondary Hypothesis 3:**

The null and alternative hypothesis to test for superiority for Comfort of the Test lens relative to the threshold 52 CLUE points are as follows:

$$H_0: \mu_{Test} \leq 52$$

$$H_A: \mu_{Test} > 52$$

Where  $\mu_{Test}$ , represents the population mean for the Test lens at the 1-week follow-up with respect to CLUE comfort scores. Superiority will be declared if the lower limit of the 95% CI is above 52.

### **Secondary Hypothesis 4:**

The null and alternative hypothesis to test for superiority for Handling of Test lens relative to the threshold 53 CLUE points are as follows:

$$H_0: \mu_{Test} \leq 53$$

$$H_A: \mu_{Test} > 53$$

Where  $\mu_{Test}$ , represents the population mean for the Test lens at the 1-week follow-up with respect to CLUE Handling scores. Superiority will be declared if the lower limit of the 95% CI is above 53.

### ***Number of Lenses Required to Achieve Optimization***

Number of lenses required to achieve lens optimization will be analyzed using a Bayesian beta-binomial model with correlated binary data.

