# Clinical Study Protocol

## Johnson & Johnson Vision Care, Inc.

the hyperope population. This will be recorded by the subject using the CLUE Follow-up Questionnaire.

3. After approximately 1-week of wear in the optimized Test lenses, the mean overall comfort score for the Test lenses will be statistically better than 52 points. This will be recorded by the subject using the CLUE Follow-up Questionnaire.
4. After approximately 1-week of wear in the optimized Test lenses, the mean overall handling score for the Test lenses will be statistically better than 53 points. This will be recorded by the subject using the CLUE Follow-up Questionnaire.
5. The percentage of subjects who obtain the optimum lens pair in 4 lenses or less will be statistically better than 90%.

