#### Lens Fit Success

Lens fit success was converted to a binary response as  $Y = 1$  if lens optimization was achieved in 4 lenses or less and  $Y = 0$  otherwise for analysis purposes. From the historical data there was 100% rate for lens fit success there for a worst-case scenario of 98% was used as the reference rate. Assuming a correlation of 0.70 between left and right eyes within the same subject, a total of 2000 replicating trials were simulated. Given the rare event binary outcome,  $Y=0$  each replicated sample was analyzed using a Bayesian beta-binomial model with correlated binary data (Diniza et al; 2010). For each simulated trial, the lower bound of the 99% central posterior credible interval constructed for the percentage successful lens fit for the Test lens was compared to a margin of 90%. With the proposed sample size, there was at least 80% of the estimated 99% credible intervals with the lower bound being above 90%.

Table 8 displays the sample size estimates and associated power by endpoints. As indicated below, co-primary safety endpoints were powered ~92% individually yielding a combined power of ~84%. With respect to co-primary efficacy each hypothesis was powered to ~99% power provided a combine power of ~95%. Therefore, the overall combined study power for co-primary safety and co-primary efficacy hypotheses is ~79% and is considered reasonable to support any conclusions from these analyses. Furthermore, secondary endpoints were powered to achieve at least 80% statistical power. This was considered to have a minimal impact on overall study power because of the multibranch gate keeping approach being implemented.

Table 8: Sample Size Estimates by Endpoint

Endpoint Type	Endpoint	Test Type	Sample Size	Power (%)
Primary Efficacy	VP - Distance	Superiority (0.00)	17	99.4
	VP - Intermediate	Superiority (0.17)	11	99.3
	VP - Near	Superiority (0.17)	48	99.0
	CLUE Vision-Hyperopes	Superiority (36)	14	99.4
	CLUE Vision Myopes	Superiority (41)	18	99.0

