#### **The Model:**

Let  $Y_1$  and  $Y_2$  denote the binary outcomes of lens fit acceptance (Yes/No) in left and right eyes, respectively, across dispensing and follow-up visits when wearing the Test lens. Considering the correlation,  $\rho$ , between  $Y_1$  and  $Y_2$ , the distribution of the sum  $Y = Y_1 + Y_2$  is obtained by the mixture of two variables. One of them follow a binomial distribution  $Bin(2, p)$  with mixing probability  $(1 - \rho)$  and the other one follows a modified Bernoulli distribution,  $MBern(p)$ , taking value 0 and 2 rather than conventional 0 and 1, with mixing probability  $\rho$ :

$$P(Y = y | p, \rho) = (1 - \rho)Bin(2, p)I_{A1} + \rho MBern(p)I_{A2},$$

where  $I_{A1} = \{0, 1, 2\}$ ,  $I_{A2} = \{0, 2\}$  and  $p$  is the probability of success (i.e., acceptable lens fitting).

To overcome the complexity of the mixture likelihood a latent variable  $Z_i, i = 1, 2$  is introduced in the model to indicate in which component of the model the observation  $y_i, i=1, 2$ , belongs to, that is,

$$Z_i = \begin{cases} 1, & \text{if the observation belong to the MBern}(p), \\ 0, & \text{if the observation belong to the Bin}(2, p) \end{cases}$$

The joint distribution of the augmented data  $(Y_i, Z_i), i = 1, 2$ , is given by

$$\begin{aligned} P(Y = y_i, Z = z_i | p, \rho) \\ = \rho^{z_i} p^{y_i z_i / 2} (1 - p)^{(2 - y_i) z_i / 2} (1 - \rho)^{1 - z_i} \binom{2}{y_i} p^{y_i (1 - z_i)} (1 - p)^{(2 - y_i) (1 - z_i)} \end{aligned}$$

The probability  $p$  links to the regression variables through a logit transformation as follow:

$$\text{logit}(p) = \beta_0 + \beta_1 \text{lens}$$

It is assumed that  $\beta_0, \beta_1$  and  $\rho$  to be independent with a non-informative prior  $N(0, 1000)$  for  $\beta_0$  and  $\beta_1$ , and  $\text{beta}(0.5, 0.5)$  for  $\rho$ . The Metropolis sampler algorithm as implemented in the SAS/STAT MCMC Procedure will be used to estimate the posterior distributions of the

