### ***Bayesian Estimation and Statistical Evaluation of Hypothesis:***

Superiority of the Test lens relative to the pre-defined threshold with respect to unacceptable lens fitting will be evaluated using Bayesian statistics. The null and alternative hypotheses for evaluating superiority of the Test lens relative to 90% are as follows:

$$H_0: p_T \leq 0.90$$

$$H_A: p_T > 0.90,$$

where  $p_T$  is the probability of event (i.e., proportion of subjects to achieve optimization in 4 lenses or less while wearing the test lens). Based on Bayesian posterior probability distribution of the proportion  $p_T$ , superiority is interpreted as 95% probability of the Test lens being statistically greater than the pre-defined threshold of 90% (i.e.,  $p_T > 0.90$ ) with respect to

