# Clinical Study Protocol

## Johnson & Johnson Vision Care, Inc.

unacceptable lens fitting rate. If the upper bound of the 95% central posterior credible interval is above 0.90, it can be concluded that there is 95% probability that the Test lens is superior to the 90% threshold (statistically better) based on the observed sample.

In the case of all eyes have an acceptable lens fit (i.e., zero event of non-optimization), a Bayesian hierarchical model accounting for zero event problem will be considered. Details of this model will be provided in the stand-alone SAP.

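### Lens-fit success is claimed per subject but powered and modelled per eye; unless both eyes share one outcome, the 90% hurdle is applied to an easier proportion

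*Combined protocol and SAP*

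**What the plan says.** **Subject level.** Section 2.3, secondary hypothesis 5: "The percentage of subjects who obtain the optimum lens pair in 4 lenses or less will be statistically better than 90" per cent. Section 14.6 defines p_T as the "proportion of subjects to achieve optimization in 4 lenses or less while wearing the test lens".

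**Eye level.** Section 14.2 (Lens Fit Success): "Assuming a correlation of 0.70 between left and right eyes within the same subject, a total of 2000 replicating trials were simulated". Section 14.6: "Number of lenses required to achieve lens optimization will be analyzed using a Bayesian beta-binomial model with correlated binary data". That model is written out only in section 14.5 (The Model), for binary outcomes "in left and right eyes, respectively, across dispensing and follow-up visits when wearing the Test lens", with p the success probability of a single eye. The zero-event rule for this endpoint also speaks of eyes: "In the case of all eyes have an acceptable lens fit (i.e., zero event of non-optimization".

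**Unit not stated.** Section 14.2 sets Y=1 "if lens optimization was achieved in 4 lenses or less", without saying whether the count belongs to an eye or to a pair.

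**Power inputs.** Section 14.2 states that "a worst-case scenario of 98% was used as the reference rate", compares the lower bound of a 99% credible interval with 90%, and sets a minimum power of 80%. Table 8 gives N=92 and 82.1%.

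**Decision rule.** Section 14.4 also specifies a 99% credible interval. Section 14.6 instead declares success when the upper bound of a 95% interval is above 0.90.

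**The concern.** Obtaining an optimum lens pair is one event per subject. If it requires success in both eyes, the subject proportion cannot exceed the eye proportion, and it is lower whenever the eyes can disagree. Comparing the per-eye p with 90% then tests a weaker statement than the one to be claimed, and the power shown is power for that weaker statement.

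The unclear lens count adds to this. Section 7.2 allows up to two modifications at Visit 1 and two at Visit 2, so an eye uses at most 1 + 2 + 2 = 5 lenses. A per-eye limit of four is missed only if every permitted modification is used. Counted over the pair, two pairs already make four lenses. These are very different endpoints under the same 90% hurdle.

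**Working it through.** **Inputs.** Correlation ρ = 0.70, assumed rate 98%, threshold 90%, 99% lower bound and N = 92 (sections 14.2 and 14.4, Table 8); 100 planned completers (section 14.2). The priors in section 14.5 are N(0,1000) on the logit scale and Beta(0.5,0.5) for ρ. They are written for the safety model; no prior is given for this endpoint, so three priors on p were tried. Assumption: a subject succeeds only if both eyes succeed.

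**Model.** From section 14.5, for one subject:

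- P(both succeed) = (1−ρ)p² + ρp
- P(exactly one) = 2(1−ρ)p(1−p)
- P(neither) = (1−ρ)(1−p)² + ρ(1−p)

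All outcomes were enumerated exactly. A trial passes if the 0.5% posterior quantile of p exceeds 0.90; zero-failure trials count as passes.

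**1. The plan's 82.1%** (N=92, eye rate 98%, ρ=0.70)

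| Eye-level variant | Power |
|---|---|
| Beta(0.5,0.5) on p | 83.7% |
| Beta(1,1) on p | 78.9% |
| N(0,1000) on logit p | 88.7% |
| Effective sample 2×92/(1+0.7) ≈ 108, at most 3 failures | 82.9% |

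With 2000 simulated trials the Monte Carlo standard error is √(0.821×0.179/2000) ≈ 0.9 points, so 82.9% and 83.7% are both compatible with 82.1%. A subject-level binomial at N=92 gives 72.0% (at most 2 failures) or 88.7% (at most 3). Neither is close.

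**2. The subject boundary in eye terms.** Solve 0.3p² + 0.7p = 0.90: p = (−0.7 + √(0.49 + 1.08))/0.6 = 0.9217.

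**3. False-pass rate at a true 90% subject rate** (ρ=0.70, N=92)

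| Prior on p | Eye model | Subject-level test | Ratio |
|---|---|---|---|
| N(0,1000) logit | 5.4% | 1.45% (≤3 failures) | 3.8 |
| Beta(0.5,0.5) | 3.9% | 0.39% (≤2 failures) | 10 |
| Beta(1,1) | 2.5% | 0.39% (≤2 failures) | 6.5 |

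At N=100 the eye model gives 6.4%, 4.1% and about 2.4% to 2.5%, against 0.78%, 0.78% and 0.2%. One outcome at each end lies almost on the pass boundary: under Beta(1,1) it decides between 2.4% and 2.5%, and under the logit prior the 6.4% would become 5.3% if it failed.

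**4. Dependence on ρ** (N=92, range over the three priors)

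| ρ | Eye-model false pass |
|---|---|
| 0.5 | 5.9–10.8% |
| 0.7 | 2.5–5.4% |
| 0.8 | 1.5–3.4% |
| 0.9 | 0.9–2.0% |
| 1 (one shared outcome) | 0.39–1.45%, equal to subject level |

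**5. Power for the subject-level claim** (Beta(0.5,0.5), 98% subject rate)

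| N | Failures allowed | Power |
|---|---|---|
| 92 | 2 | 72.0% |
| 97 | 2 | 69.3% |
| 98 | 3 | 86.6% |
| 100 | 3 | 85.9% |

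If 98% is instead an eye rate with ρ=0.70, the subject rate is 0.3×0.98² + 0.7×0.98 = 0.9741, and power at N=100 is about 74%.

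**6. The section 14.6 rule read literally.** An upper 95% bound above 0.90 passes about 98% of the time at a true 90% (N=92, subject level, Beta(0.5,0.5)).

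**The case against.** The best defence is that Y may not be scored per eye at all. Section 14.2 names no eye in defining Y here, whereas it does for slit-lamp findings, and the mandatory modification triggers in section 7.2 are the subject's own report of unsatisfactory vision or binocular acuity. If one pair-level result is carried to both eyes, there is no inflation. That stands, and it makes the false-pass result conditional. It does not rescue the plan: a shared outcome contradicts the 0.70 correlation, so the 82.1% then has no valid basis.

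The 0.70 is also only a planning value. The model estimates ρ from the data, and at 0.9 the rise is about 1.4 to 3 times. That stands too.

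A reader might infer that 82.1% cannot be reproduced. The documents do not support this: only the logit prior of section 14.5 gives a clearly different figure, and that prior is not stated for this endpoint.

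The fitting guide is redacted and some detail is deferred to a stand-alone SAP, so the counting rule may exist elsewhere. The hypothesis and the model still disagree in the text available.

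Finally, the stakes are limited. This is one of five secondary hypotheses, tested only after all seven co-primary hypotheses are met, and historical success was 100% (Table 7).

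**Conclusion.** The unit mismatch is in the text and should be resolved. If eyes are scored separately and a subject needs both, the test is anti-conservative for the stated claim: at ρ=0.70 and N=92 the false-pass rate is about 4 to 10 times that of a subject-level test with the same prior. The rise is larger at ρ=0.5, small at 0.9 and absent if both eyes always share one outcome. A reader might take a several-fold rise, or the 6.4% at N=100, as established. Neither is: the first depends on per-eye scoring and on ρ, and the second is the highest of three priors.

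The 82.1% is approximately an eye-level power. For the claim as worded, power at N=92 is 72.0% with Beta(0.5,0.5), below the plan's 80% minimum. All false-pass figures in the tables use the 99% lower-bound rule of sections 14.2 and 14.4, not the conflicting rule in section 14.6, which taken literally is the larger fault.

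**What to change.** 1. Define one binary outcome per subject, and state in section 2.3 whether the four lenses are counted per eye or over the pair.
2. Analyse with a subject-level beta-binomial, Beta(0.5,0.5) prior. Alternatively, keep the eye model and test the derived (1−ρ)p² + ρp against 0.90.
3. Use the lower bound of the 99% interval in sections 14.2, 14.4 and 14.6, replacing the upper-bound 95% rule.
4. For the subject-level analysis, drop the 0.70 correlation and restate power at 100 completers with its assumption: about 86% if 98% is the subject rate, about 74% if it is an eye rate with ρ=0.70. Note that power falls to about 69% at 97 completers even with a 98% subject rate, because one fewer failure is then allowed. The 86% should not be presented as a stable figure.

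The cost is wording plus a short power restatement before the SAP is final. The downside is lower stated power: like for like with Beta(0.5,0.5), 83.7% becomes 72.0% at N=92, and 90.2% becomes 85.9% at N=100 if 98% is taken as the rate for each unit.
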